11.2.7.2 Handling of missing data

As the PDS includes all subjects who received at least 4 weeks of study treatment with at least one valid lymphocyte measurement on or after the Week 4 assessment, all available data at the visits of interest (Week 4, Week 8 and Week 12) will be included in the analysis. Thus, data of subjects with one, two or three post-baseline measurements at the predefined time points will contribute to the dose-response analysis. Every effort will be made to collect lymphocyte data, as complete as possible, for every subject at every visit. Last observation carried forward (LOCF) will be used as a sensitivity analysis as described below.

11.2.7.3 Main analysis of the primary PD variable (primary analysis)

To meet the objective of demonstrating existence of an intra-subject dose response on the absolute lymphocyte count reduction from baseline in subjects with GVHD, at least one null hypothesis must be rejected with a one-sided significance level of 5%. The type-1 error will be controlled via a hierarchical ordering of the tests: pairwise comparisons will be conducted in decreasing dose order. Within-subject t-tests will be performed at each dose level (assuming normally distributed data).

In addition, an E_{\max} model will be fitted for the baseline, Week 4, Week 8 and Week 12 data. The data will be summarized with point-wise and model-based estimates, standard deviation and 95% CIs on the reduction in absolute lymphocyte counts from baseline at the examined dose levels. A plot of the estimated dose-response curve with 95% credibility interval limits will be presented along with the observed response at each dose.

The primary analysis will be performed on the PD analysis set and conducted after the last patient has completed the Follow-Up 1 visit in the Core Treatment Period.

11.2.7.4 Supportive/sensitivity analyses

A sensitivity analysis of the primary analysis will be performed on the FAS (in case the FAS does not contain the same number of subjects as the PDS).

Further t-tests will be performed across dose levels (5 mg vs 10 mg, 5 mg vs 20 mg and 10 mg vs 20 mg). These tests, performed at a one-sided significance level of 5%, will be

considered as exploratory. These pairwise comparisons will be performed on the FAS and PDS.

An LOCF approach (using the Week 4 visit or later) will be performed for subjects with a missing Week 8 or Week 12 assessment, based on the FAS.

The dose-response modeling will be repeated using the Week 4, Week 8 and Week 24 assessment (instead of the Week 12 assessment), based on the PDS.

11.2.7.5 Subgroup analyses

No subgroup analyses are planned due to small sample size.

11.2.8 Analysis of the efficacy variables

The analyses of all exploratory endpoints will be based on the PPS and FAS, if applicable. The following binary endpoints will be summarized descriptively as described in Section 11:

- Achievement of a partial or complete overall response at 24 weeks (per NIH Consensus Development Project response criteria)
- Need for rescue therapy for chronic GVHD
- Partial or complete organ-specific response for the specific organ manifestation at Week 12 and Week 24 in subjects with a specific organ manifestation of chronic GVHD
- Partial or complete overall response at Week 12
- Complete response at Week 24
- Partial or complete overall response at latest evaluable assessment during the core study (Week 12 and Week 24)

The remaining two exposure-related, continuous endpoints will be analyzed based on summary statistics as described in Section 11:

- Average glucocorticoid daily dose over 24 weeks versus baseline dose
- Percent glucocorticoid dose at Week 24 versus baseline

11.2.9 Analysis of the efficacy variables during the Extension Treatment Period

The analyses of all exploratory endpoints will be based on the ES.

All efficacy variables will be summarized descriptively, by visit, based on the ES. If subject numbers drop below a certain threshold only listings will be provided. No statistical tests will be applied to any of these endpoints.

Confidential

The endpoint “Achievement of a partial or complete overall response at 24 weeks (per NIH Consensus Development Project response criteria)” will be analyzed at Week 24 and Week 96 in the Extension Treatment Period and selected other time points.

The endpoint “Need for rescue therapy for chronic GVHD” will be analyzed throughout 96 weeks of treatment or up to premature discontinuation.

The endpoint “Partial or complete organ-specific response for the specific organ manifestation at Week 12 and Week 24 in subjects with a specific organ manifestation of chronic GVHD” will be assessed at Weeks 12, 24, and 96 in the Extension Treatment Period and selected other time points.

The endpoint “Partial or complete overall response at Week 12” will also be analyzed at Week 12 in the Extension Treatment Period.

The endpoint “Complete response at Week 24” will be assessed at Week 24 and Week 96 in the Extension Treatment Period and selected other time points.

The endpoint “Partial or complete overall response at latest evaluable assessment during the study” will be extended to the whole Extension Treatment Period.

The exposure related endpoints will be analyzed based on summary statistics. Both endpoints “Percent glucocorticoid dose at Week 24 versus baseline” and “Average glucocorticoid daily dose over 24 weeks versus baseline dose” will be analyzed at the end of treatment visit (EOT2) in the Extension Treatment Period, and compared to the baseline visit of the Extension Treatment Period (Visit EX-1).

If there are not enough subjects in the ES population, only listings will be provided.

11.2.10 Analysis of the safety variable(s)

All safety analyses will be conducted on data up to 30 days (inclusive) after last study drug intake for the Core Treatment Period and for the Extension Treatment Period. All AEs will be coded using the latest version of MedDRA available at the time of database closure.

11.2.10.1 Adverse Events

11.2.10.1.1 Treatment-emergent AEs, SAEs, and AEs of special interest

Treatment-emergent AEs and SAEs will be tabulated by system organ class (SOC) and preferred terms within each SOC: the number and percentage of subjects who experienced at least one (S)AE, at least one (S)AE within each SOC and at least one S(AE) within each preferred term will be displayed. (S)AEs will also be summarized by decreasing frequency of preferred term. (S)AEs will also be tabulated by maximum intensity.

AEs of special interest will be summarized in the same way as stated above.

Confidential

Treatment-emergent AEs and SAEs and AEs of special interest will be analyzed for the Extension Treatment Period as described above.

11.2.10.1.2 AEs leading to premature discontinuation of study drug

(S)AEs leading to premature discontinuation of study drug will be summarized in a similar manner as described above.

(S)AEs leading to premature discontinuation of study drug will be summarized for the Extension Treatment Period as described above.

11.2.10.1.3 Deaths

Fatal SAEs occurring any time after the start of treatment will be summarized in a similar manner as described above. Fatal SAEs will also be summarized for the Extension Treatment Period.

11.2.10.2 Absolute lymphocyte count

Data of subjects with treatment-emergent absolute lymphocyte count $< 0.2 \times 10^9/L$ (< 200 cells/mm 3) will be summarized descriptively for the Core Treatment Period and for the Extension Treatment Period.

11.2.10.3 Cardiac Safety

11.2.10.3.1 Treatment-emergent morphological ECG abnormalities (as defined by the ECG provider)

Treatment-emergent morphological ECG abnormalities will be summarized descriptively for the Core Treatment Period and for the Extension Treatment Period.

11.2.10.3.2 12-lead ECG assessments

Descriptive summary statistics, by time and visit, will be provided for observed treatment-emergent values and absolute changes from baseline in numeric 12-lead ECG values (HR, PR, QRS, QT, QTcB and QTcF). Data will be summarized from pre-dose to the post-dose assessments at 1 h, 2 h, 3 h and 4 h on Day 1. 12-lead ECG data will also be summarized for the Extension Treatment Period.

11.2.10.3.3 Notable abnormalities for selected 12-lead ECG variables

Notable abnormalities for selected 12-lead ECG variables (HR, PR, QT, QTcF) will be summarized for all data at the 3-hour post dose assessments on Day 1 and pre-dose at Weeks 4, 8, 12, and 24. Notable abnormalities will also be summarized for the Extension Treatment Period.

11.2.10.3.4 Cardiac safety events

Cardiac safety events will include:

Confidential

- Treatment-emergent QTc > 450 ms (male), > 470 ms (female), > 500 ms (male), and > 520 ms (female)
- Treatment-emergent QTc increase from baseline > 30 ms, > 60 ms
- Other treatment-emergent abnormalities observed by 12-lead ECG
- Treatment-emergent (serious) cardiac AEs of special interest.

Cardiac safety events will be summarized descriptively for the Core Treatment Period and for the Extension Treatment Period.

11.2.10.4 Pulmonary safety

11.2.10.4.1 PFT

Descriptive summary statistics by visit will be provided for observed treatment-emergent values and changes from baseline by visit in FEV₁, FVC and FEV₁/FVC ratio (all expressed in absolute change, % change and % change of percent predicted value).

The number and proportions of treatment-emergent decreases of FEV₁ or FVC and percent predicted FEV₁ or FVC > 20% from baseline up to Week 24 will be summarized.

Reversibility of pulmonary parameters will be analyzed at the last available follow-up visit. The analysis will summarize subjects still showing a decrease of > 200 mL in FEV₁ and FVC or a change in FEV₁ and FVC of > 12% from baseline at the follow-up visit among subjects with a decrease of > 200 mL or > 12% in FEV₁ or FVC from baseline to EOT1.

The mean (and 95% CIs) change from baseline to FU1 and from baseline to EOT1 in FEV₁ or FVC (absolute and % predicted) will be summarized and plotted. A scatter plot will display the change from baseline to EOT1 versus the change from baseline to FU1 on an individual subject level.

PFT data will be analyzed in a similar manner during the Extension Treatment Period.

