6.2.4 Pulmonary function safety endpoints

- Treatment-emergent decrease of FEV₁ or FVC $> 20\%$ from baseline values
- Treatment-emergent decrease of percent of predicted FEV₁ or FVC > 20 percentage points from baseline values
- Change in FEV₁ and FVC from baseline, absolute and % of absolute change to all time points up to FU1

Confidential

- Among subjects with a decrease of > 200 mL and > 12% in FEV₁ or FVC from baseline to EOT1, reversibility is defined as a decrease of < 200 mL or < 12% in FEV₁ or FVC, respectively, from baseline to last available follow-up
- Change from baseline to FU1 vs change from baseline to EOT1 in FEV₁ or FVC (absolute and % of predicted)
- Change in lung diffusion capacity as assessed by the DL_{CO}, expressed in absolute change and % of predicted value from baseline to all time points up to FU1
- Change from baseline to FU1 vs change from baseline to EOT in DL_{CO} (absolute and % of predicted)
- (Serious) pulmonary AEs of special interest
- Withdrawal due to pulmonary reasons/AE

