11.2.2 Safety variables

The following safety endpoints/variables will be analyzed. The SAP will summarize these analyses in more detail. Safety endpoints will be analyzed from first study drug intake up to 30 days (inclusive) after last study drug intake.

Overall safety endpoints

- Treatment-emergent AEs, SAEs, and AEs of special interest
- AEs leading to premature discontinuation of study drug
- Deaths

Absolute lymphocyte count

- Treatment-emergent absolute lymphocyte count $< 0.2 \times 10^9/L$ ($< 200 \text{ cells/mm}^3$)

Cardiac rate and rhythm safety endpoints

- Treatment-emergent morphological ECG abnormalities
- Change in 12-lead ECG variables (HR, PR, QRS, QT, QTcB, QTcF) from pre-dose to selected post-dose assessments (1h, 2h, 3h, 4h) on Day 1 and on day(s) of re-initiation of study drug
- Notable abnormalities for selected 12-lead ECG variables (HR, PR, QT, QTc) at 3 h post-dose assessment on Day 1 and pre-dose on Weeks 4, 8, 12, and 24 (notable abnormalities definition in Appendix 6)
- Cardiac safety events will include:
 - Treatment-emergent QTc $> 450 \text{ ms}$ (male), $> 470 \text{ ms}$ (female), $> 500 \text{ ms}$ (male), and $> 520 \text{ ms}$ (female)
 - Treatment-emergent QTc increase from baseline $> 30 \text{ ms}$, $> 60 \text{ ms}$
 - Other treatment-emergent abnormalities observed by 12-lead ECG
 - Treatment-emergent (serious) cardiac AEs of special interest.

Confidential

Pulmonary function safety endpoints

- Treatment-emergent decrease of FEV₁ or FVC > 20% from baseline values
- Treatment-emergent decrease of percent of predicted FEV₁ or FVC > 20% from baseline values
- Change in FEV₁ and FVC from baseline, absolute and % of absolute change to all visits up to FU1
- Among subjects with a decrease of > 200 mL and > 12% in FEV₁ or FVC, respectively, from baseline to EOT1, reversibility defined as a decrease of < 200 mL and < 12% in FEV₁ or FVC, respectively, from baseline to last available follow-up
- Change from baseline to FU1 vs change from baseline to EOT1, in FEV₁ or FVC (absolute and % of predicted)
- Change in lung diffusion capacity as assessed by DL_{CO} expressed in absolute change and % of predicted value from baseline to all time points up to FU1
- Change from baseline to FU1 vs change from baseline to EOT1 in DL_{CO} (absolute and % of predicted)
- (Serious) pulmonary AEs of special interest
- Withdrawal due to pulmonary reasons/AE

Other safety endpoints

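### The proportion of subjects with lung-function reversal is biased upward by regression to the mean, and the plan gives no interval for the within-subject recovery that would answer the question

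*Combined protocol and SAP*

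**What the plan says.** Under 11.2.10.4.1, "Reversibility of pulmonary parameters will be analyzed at the last available follow-up visit". The denominator is defined as "among subjects with a decrease of > 200 mL or > 12% in FEV₁ or FVC from baseline to EOT1". Persistence is described this way: "The analysis will summarize subjects still showing a decrease of > 200 mL in FEV₁ and FVC or a change in FEV₁ and FVC of" more than 12% at follow-up.

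The same endpoint is worded differently elsewhere:

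| Section | Entry at EOT1 | Reversed or persistent at follow-up |
|---|---|---|
| Synopsis; 11.2.2 | > 200 mL *and* > 12% | reversed if < 200 mL *and* < 12% |
| 6.2.4 | > 200 mL *and* > 12% | reversed if < 200 mL *or* < 12% |
| 11.2.10.4.1 | > 200 mL *or* > 12%, in FEV1 *or* FVC | persistent if > 200 mL *or* > 12%, in FEV1 *and* FVC |

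Section 11.2.2 has "reversibility defined as a decrease of < 200 mL and < 12% in FEV₁ or FVC, respectively, from baseline to last available follow-up", while 6.2.4 has "reversibility is defined as a decrease of < 200 mL or < 12% in FEV₁ or FVC, respectively, from baseline to last available follow-up".

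The next paragraph of 11.2.10.4.1 has no entry threshold. It plans to summarize and plot "The mean (and 95% CIs) change from baseline to FU1 and from baseline to EOT1 in FEV₁ or FVC (absolute and % predicted"), and adds: "A scatter plot will display the change from baseline to EOT1 versus the change from baseline to FU1 on an individual subject level". Sections 6.2.4 and 11.2.2 list the comparison of the FU1 change with the EOT1 change as a separate endpoint. Baseline is the Day 1 measurement (7.3.3).

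**The concern.** Subjects enter the denominator because one EOT1 reading was low relative to one Day 1 reading. Part of that gap is measurement error: an unusually low EOT1 value, an unusually high baseline, or both. The EOT1 part of the error does not recur at follow-up, so the follow-up fall is smaller on average even if the true lung function has not moved. Some of the apparent reversal is therefore built in. The documents give no noise benchmark, confirmatory reading or comparator against which to judge the proportion.

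Safety and tolerability are a main objective (2.1). The rationale for Amendment 3 relies on reversibility seen in MS patients when it widens lung-function eligibility. A statement that most affected subjects reversed, drawn from a few selected subjects, would be read as confirming this in chronic GVHD.

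**Working it through.** **Plan's own figure.** None is given for reversibility, so there is nothing to reproduce.

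**Inputs from the documents.** Cut-offs as above; one Day 1 baseline (7.3.3); mean FEV1 fall of about 6% on 20 mg in MS patients (Amendment 3 rationale); about 30 subjects (3.1).

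**Assumed, not in the documents.** True FEV1 F = 2.5 L (2.0-3.0); visit-to-visit SD s = 0.15 L (0.10-0.20), independent between visits; between-subject SD of the drug effect 5% of F; 25 subjects with both EOT1 and FU1 for the paired analysis. FEV1 only.

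**Model.** Each visit equals the true value plus error. The falls to EOT1 and to follow-up share the baseline error. With no drug effect each fall has SD √2 × 0.15 = 0.212 L, and their correlation is s²/(2s²) = 0.5.

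**Closed form for the *or* cut-offs of 11.2.10.4.1.** At 2.5 L, 12% is 0.30 L, so 200 mL sets the *or* rule.

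- *No effect.* z = 0.200/0.212 = 0.943. Qualifying: 1 − Φ(0.943) = 17% (about 5 of 30). Reversed given qualifying: 1 − P(Z1 > 0.943, Z2 > 0.943; ρ = 0.5)/0.173 = 59%.
- *Lasting fall.* Mean 0.06 × 2.5 = 0.15 L; SD √(2 × 0.15² + 0.125²) = 0.246 L; z = (0.20 − 0.15)/0.246 = 0.203; 42% qualify (about 13 of 30). ρ = (0.0225 + 0.0156)/0.0606 = 0.63; reversed 33%.
- *Fully reversible fall.* Same qualifiers; the follow-up fall has mean 0 and SD 0.212, ρ = 0.0225/(0.246 × 0.212) = 0.43; reversed 72%.

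**Other wordings.** Simulation of 2,000,000 subjects per scenario, with percentages taken relative to the observed baseline. Base case:

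| Rule (entry / reversed) | No effect: qualify, reversed | Lasting 6% fall: qualify, reversed | Reversible 6% fall: reversed |
|---|---|---|---|
| *and* / *and* (Synopsis, 11.2.2) | 7%, 52% | 26%, 26% | 68% |
| *and* / *or* (6.2.4) | 7%, 76% | 26%, 46% | 86% |
| *or* cut-offs (11.2.10.4.1) | 17%, 59% | 42%, 33% | 72% |

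Over the assumed grid, the no-effect reversal is 44-67%, 62-93% and 53-71% for the three rows. Reading 11.2.10.4.1 literally, with persistence required in both FEV1 and FVC, pushes the proportion higher still, because that is a harder standard than the entry rule.

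**What a paired estimate would give.** Recovery = FU1 − EOT1 within subject, so the baseline error cancels. For n = 25 and a reversible 6% fall, the 95% CI half-width is 2.064 × 0.246/√25 = 0.10 L, against an expected recovery of 0.15 L. In simulated trials:

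- the lower limit is above zero in 83% (97% and 64% at s = 0.10 and 0.20 L), and in 2.5% if the fall is lasting;
- the two separate CIs that the plan provides fail to overlap in only about 24% of trials in the same base case.

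**Who contributes.** FU1 is cancelled when EX-1 falls on or before it (Synopsis, 3.2.3; Table 1 note 8), and extension entry requires GVHD progression (4.6). Table 1 schedules spirometry at FU1 but not at FU2. The EOT1 mean can therefore include subjects absent from the FU1 mean, and this loss is related to disease course.

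**The case against.** The strongest reply is that the plan does not depend on the selected subset. It has unselected mean changes with 95% CIs, an individual scatter plot, and a separate endpoint comparing the two changes. In subjects with both visits, the difference between the two means is the mean recovery, so only its interval is missing. This stands. A reader might infer that reversibility is judged only in selected subjects; the documents do not support that.

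A reader might also infer that the proportion cannot show reversal at all. That is too strong: it moves from 26% to 68%, or from 33% to 72%, between a lasting and a reversed effect. Nor is chance reversal in half or more of qualifiers the general case. It belongs to the no-effect scenario, where only about 2 to 5 of 30 subjects would qualify. With a lasting 6% fall the base-case figures are below half.

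Nor does this table separate a drug effect from bronchiolitis obliterans syndrome. Section 5.1.10.7 does that subject by subject, through bronchodilator challenge and spirometry after discontinuation. The safety analyses are mainly descriptive, and no success criterion is attached to the proportion.

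The paired estimate has limits too. Subjects without FU1 are not a random subset, and treatment after EOT1 follows local standard of care (3.2.2), which may contribute to any change.

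What survives is the upward bias, the missing interval, the possible mismatch of subjects between the two means, and the inconsistent rule.

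**Conclusion.** The point holds as a modest improvement to a descriptive safety analysis. The proportion reversed is biased toward reversal under every wording examined, and it has no benchmark. In the base case, noise alone reverses 52-76% of qualifiers, and a lasting 6% mean fall is still called reversed in 26-46%, against 68-86% if fully reversible. These figures rest on an assumed FEV1, visit SD and between-subject effect SD. The direction of the bias does not depend on those values; its size does. The unselected outputs escape the selection, but separate intervals around two changes that share a baseline are an insensitive way to judge recovery. The proportion should not carry the conclusion on reversibility.

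**What to change.** In 11.2.10.4.1:

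1. Make the main reversibility result the within-subject change from EOT1 to FU1 in FEV1 and FVC (absolute and % predicted), with a 95% CI, in all subjects with both values.
2. Report how many subjects lack FU1 because they entered the extension, and note that standard of care after EOT1 may contribute to the change.
3. Keep the threshold-based proportion as a descriptive listing, stating that it is subject to regression to the mean.
4. Use one and/or rule for entry and reversal, and one rule for combining FEV1 and FVC, in the Synopsis, 6.2.4, 11.2.2 and 11.2.10.4.1.

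The cost is wording and one extra table. No visit or test is added. The downside is that the proportion reversed is no longer available as a headline result.

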11.2.10.4.2 Lung diffusion capacity (DLco)

Descriptive summary statistics and changes from baseline by visit will be provided for observed treatment-emergent values and changes from baseline (expressed in absolute change and % of predicted value) in DLco. In addition the DLco change from baseline to FU1 versus change from baseline to EOT1, expressed in absolute change and percent of predicted values change, will be summarized. DLco data will be analyzed in a similar manner during the Extension Treatment Period.

11.2.10.4.3 Pulmonary safety events

Pulmonary safety events will include:

- Treatment-emergent decrease of FEV₁ or FVC > 20% from baseline values

Confidential

- (Serious) pulmonary AEs of special interest
- Withdrawal due to pulmonary reasons/AE

Pulmonary safety events will be summarized descriptively for the Core Treatment Period and for the Extension Treatment Period.

11.2.10.5 Vital signs

Descriptive summary statistics by visit will be provided for observed treatment-emergent values and absolute changes from baseline in HR, BP and body weight.

Treatment-emergent notable BP abnormalities will also be summarized. Vital signs data will be analyzed for the Core Treatment Period and for the Extension Treatment Period.

11.2.10.6 Laboratory

11.2.10.6.1 Laboratory tests

For the Core Treatment Period, descriptive summary statistics by visit will be provided for observed treatment-emergent values and absolute and percent changes from baseline for laboratory tests (hematology, blood chemistry, urinalysis). Data will be displayed in SI units whenever possible and graphical approaches will be applied.

Laboratory data will be analyzed in a similar manner for the Extension Treatment Period.

